7.7. Exploratory Analyses

These analyses are hypothesis-generating and are not adjusted for multiple comparisons. Full results of these analyses, including interaction term estimates, standard errors, and 95% confidence intervals will be reported.

7.7.1. Protocol Deviations

For the per protocol analysis, we restrict physicians in the game-based training group to those who completed at least 2 hours of game play and include all the physicians in the usual education group. We will then repeat the primary analysis, with the endpoint of under-triage.

Protocol Deviation (Version 1.4). We add a CACE analysis to test the effect of study compliance on the magnitude of the treatment effect. We reclassify physicians in the game-based training group who never access the game and physicians in the usual education group who access the game as non-compliers, and then estimate the effect of the intervention among physicians who comply with their assigned treatment using an instrumental variable approach, with treatment assignment as the instrument.

7.7.2. Heterogeneity of treatment effect

Heterogeneity of treatment effect is evaluated through a series of pre-specified subgroup analyses. Each analysis adds an interaction term between the treatment arm and the moderator of interest to the primary GLMM. The moderators examined are sex (male vs. female), race/ethnicity (White vs. non-White), pre-enrollment attitudes toward game-based learning (play games for fun versus not).

7.7.3. Mediation of the game's effect on under-triage

We test 4 mediators of the treatment effect: intervention dose (≥ 2 hours versus < 2 hours), timing of game use–treatment of patient (≤ 30 days versus 39-90 days versus > 90 days versus none), and fidelity of intervention receipt (perceptual sensitivity and decisional threshold). To evaluate exposure–effect relationships, we model the probability of under-triage and included an interaction term between the mediator and patient injury severity. To evaluate fidelity of intervention receipt relationships, we conduct a causal mediation analysis to assess whether the effect of the intervention on under-triage is mediated through perceptual sensitivity (i.e., diagnostic ability – targeted by the game) or by decisional threshold (i.e., willingness to transfer). The total effect of the intervention is decomposed into natural direct and natural indirect effects representing pathways independent of and operating through the mediator.

Protocol Deviation (Version 1.5): We deferred the mediation analysis testing the influence of fidelity of intervention receipt because we could not obtain the correct statistical package to run the analysis on the CMS Virtual Desktop. We also reconceptualized dose as the number of intervention periods during which game play occurred for any amount of time (out of 4 total). Dose therefore represented actual treatment and not assignment.

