Secondary (outcome analysis) - The proportion of patients over-triaged by physicians in the game-based training group will be equivalent to the proportion over-triaged by physicians in the usual care group

Secondary (mediation) - Under-triage will mediate the effect of the intervention on patient-centered outcomes.

Exploratory (heterogeneity of treatment effect) -

- [1] The intervention will have the same effect on males as on female trial participants.
- [2] The intervention will have the same effect on White compared as on non-White trial participants.
- [3] The intervention will have a greater effect on trial participants who expressed positive attitudes to game-based learning before enrollment compared to those who do not have positive attitudes.
- [4] Trial participants in the game-based training group who use Night Shift 2024 for greater than 2 hours will under-triage a smaller proportion of severely injured patients than those who use the game for less than 2 hours.
- [5] The proportion of patients under-triaged by trial participants will be lower immediately after exposure to the intervention (i.e., in the first 30 days) compared to late post-exposure period (i.e., 30-89 days).
- [6] Trial participants with greater parameters of compliance on SONAR (the experimental tool to measure determinants of physicians' decision making) will under-triage a smaller proportion of severely injured patients than those with lower parameters of compliance.

**2. \* Describe the relevant prior experience and gaps in current knowledge including preliminary data. Provide for the scientific or scholarly background for, rationale for, and significance of the research based on existing literature and how it will add to existing knowledge:**

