5.3.2. Mechanisms of action

We will evaluate mediators of the game effect:

- Fidelity of intervention delivery:
 - Dose of intervention (game usage greater than vs. less than 2 hours)
 - Timing between exposure – treatment of patient (first 30 days post-usage vs. days 30-89 versus 90+ days)
- Fidelity of intervention receipt – high versus low perceptual sensitivity; high versus low decisional threshold)

Protocol Deviation (Protocol Deviation 1.5): We changed our classification of "dose" for this analysis from time ≥ 2 hours or < 2 hours to participation in game usage during each intervention period for any amount of time (4 total). We deferred evaluation of mediation by fidelity of intervention receipt because we could not download the needed statistical package to the CMS Virtual Desktop.

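### The dose and timing analyses are labelled mediation, but the only term named is an interaction with injury severity, and the contrasts for hypotheses 4 and 5 are left unspecified

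*SAP*

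**What the plan says.** The protocol (Study Aims) states two simple exposure hypotheses. Under hypothesis 4, game-arm physicians with more than 2 hours of play "will under-triage a smaller proportion of severely injured patients than those who use the game for less than 2 hours". Under hypothesis 5, under-triage is lower in the first 30 days after exposure than in days 30–89. Neither mentions injury severity.

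SAP 5.3.2 introduces dose and timing with "We will evaluate mediators of the game effect", and SAP 7.7.3 repeats the label: "We test 4 mediators of the treatment effect". For dose and timing, 7.7.3 then gives one sentence of method: "we model the probability of under-triage", and the model "included an interaction term between the mediator and patient injury severity". It does not state the contrast of interest, the arm or arms analysed, how severity is coded, or any confounder adjustment.

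The decomposition into direct and indirect effects is attached to a different analysis: "To evaluate fidelity of intervention receipt relationships, we conduct a causal mediation analysis". Version 1.5 deferred that analysis. The same version redefined dose as the number of intervention periods, out of four, with any play, and added: "Dose therefore represented actual treatment and not assignment".

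**The concern.** An interaction between dose and severity asks whether the dose effect is larger in some patients than in others. That is effect modification. Hypotheses 4 and 5 ask whether under-triage differs by dose or by recency of play, and mediation asks how much of the effect of assignment passes through dose. The one named term answers neither question.

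A reader who looks at the interaction alone could conclude that dose does nothing when it works equally at every severity, or that dose matters when its average effect is close to nil. A reader who trusts the label could take a comparison of self-selected players as evidence of mechanism. Version 1.5 deferred mediation by fidelity of receipt and dropped mediation of clinical outcomes. Dose and timing are therefore the only quantitative mechanism analyses left, and the SAP appendix lists them under mediation in the manuscript.

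**Working it through.** The documents give no sample size, effect or power for these analyses, so there is no figure to reproduce. The check is of logic, with illustrative numbers.

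**1. What the term estimates.** With dose D and severity S, the model is logit P(under-triage) = β0 + β1·D + β2·S + β3·D·S, plus a physician intercept. The effect of one unit of dose at severity s is β1 + β3·s. Hypotheses 4 and 5 concern that quantity averaged over severely injured patients. The interaction is β3 alone. A mediation estimate would also need the path from assignment to D and a split into direct and indirect effects; neither is written for dose or timing.

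**2. Large-sample illustration.** Assumed: 200,000 patients, binary dose, ISS = 16 + gamma(shape 1.5, scale 4), intercept 1.2, slope −0.03 per centred ISS point, no clustering, main effects included.

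| True dose log-OR at mean ISS | True interaction | Estimated interaction | Standardised risk difference |
|---|---|---|---|
| −0.45 | 0 | 0.000 | −8.8 points (raw −8.8) |
| 0 | −0.04 | −0.043 | −0.5 points |

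The interaction can be zero when dose works, and clearly non-zero when dose does almost nothing on average. But the same fit recovers the exposure effect by standardisation.

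Severity might instead be coded severe versus minor across all patients, with transfer as the outcome. With an equal true log-OR of 0.4 in both groups, the interaction is −0.03, while the simple effect in severe patients is 0.40 (under-triage −7.8 points). The conclusion is the same.

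**3. Realistic sample size.** Assumed: 600 severe patients, dose 0–4 with equal probability, logit = 0.9 − 0.15·dose − 0.03·(ISS − 20), ISS = 16 + exponential with mean 4 or 8, no clustering, 1,500 datasets per setting. For scale, SAP 7.2's 75% of 400 physicians per arm is 300. At 1–2 patients each that is about 300–600 game-arm patients, so 600 is the upper end.

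| Test at 0.05 | Mean excess ISS 4 | Mean excess ISS 8 |
|---|---|---|
| Dose, no interaction in model | 0.68 | 0.68 |
| Interaction term | 0.05 | 0.06 |
| Dose coefficient, interaction kept, ISS centred | 0.68 | 0.69 |
| Dose coefficient, interaction kept, ISS uncentred | 0.07 | 0.13 |

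The interaction rejects at about the chance rate because none was simulated. With ISS uncentred, the dose coefficient is the effect at ISS = 0, outside an endpoint defined by ISS ≥16. Its standard error grows by about √(1 + (mean/SD)²): √(1 + (20/4)²) = 5.1 and √(1 + (24/8)²) = 3.2. The simulation gave 5.2 and 3.2. With ISS centred, the ratio is 1.00.

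**4. Definitions side by side.**

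| | Protocol hypotheses 4 and 5 | SAP 5.3.2 | SAP 7.7.3 |
|---|---|---|---|
| Dose | >2 h vs <2 h, game arm | >2 h vs <2 h; from Version 1.5, any play in each of 4 periods | ≥2 h vs <2 h; from Version 1.5, number of periods with any play, out of 4 |
| Timing | first 30 days vs days 30–89 | first 30, 30–89, 90+ days | ≤30, 39–90, >90 days, none |

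Under Version 1.5, a physician who opens the game briefly in every period scores 4 without reaching 2 hours. One who completes 2 hours at the start and skips every booster scores 1. The new scale can therefore reverse the ordering in hypothesis 4. In 7.7.3, days 31–38 (38 − 31 + 1 = 8 days) belong to no bin, and day 90 falls in the middle bin where 5.3.2 puts it in the last.

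**5. Self-selection.** Dose and timing arise after randomisation, from the physician's own choice. If both arms are pooled, zero dose mixes usual-education physicians with game-arm physicians who never played. The SAP does not say whether they are pooled.

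**The case against.** The strongest reply is that the interaction is only one component of the model. The stated aim is the exposure–effect relationship, the text says the interaction was included and not that it was the sole coefficient tested, and SAP 7.7 promises full results. A conventional fit has main effects, and with ISS centred the check above shows no loss of power. Severity is also a reasonable modifier of a triage decision. All of this stands.

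A reader might infer that this model cannot answer hypotheses 4 and 5, or that power collapses to roughly 10%. The documents support neither reading. The collapse occurs only if the coefficient at ISS = 0 is reported, and the SAP does not say that ISS is continuous, uncentred or read that way.

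It can also be said that mediation is only a label, since 7.7.3 gives dose and timing an exposure–effect model and states that dose is actual treatment. That goes part of the way, but both 5.3.2 and 7.7.3 call them mediators, and no confounder adjustment is stated.

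The per-protocol and complier analyses in 7.7.1 also examine exposure. The first compares players of at least 2 hours with all usual-education physicians; the second treats never accessing the game as non-compliance. Neither compares more with less than 2 hours within the game arm. The 39 in the timing bins may be a typing error, but the text as it stands leaves a gap.

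**Conclusion.** The point holds in a limited form. For dose and timing, the only term the SAP names is effect modification by severity, the contrast that would answer hypotheses 4 and 5 is not stated, and the mediation label is unsupported for a self-selected exposure. Hypothesis 4 as written is not measured by the Version 1.5 dose, and the timing bins conflict between sections and omit eight days. These last two findings rest on the text alone.

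The numerical size depends on the coefficient reported. Under the assumed inputs, the same data and model give power of about 68% or about 7–13%, depending on whether ISS is centred. Sample size, effect and ISS distribution are all assumptions, and clustering is ignored.

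The revision table dates the dose change to 3 October 2025, two days after data lock. A reader might infer that the definition was chosen on its results; the documents do not show that, and they give better understanding of mediation as the reason.

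The analyses are declared hypothesis-generating, so the consequence is confined to the mechanism claims.

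**What to change.** In SAP 7.7.3, replace the interaction sentence with the following:

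- Among patients with ISS ≥16 treated by game-arm physicians, fit the physician-level GLMM with dose (or timing) as the term of interest. Adjust for ISS and the patient and physician baseline covariates listed in 7.5.
- Report predicted under-triage at each level with 95% CI, and the contrast that corresponds to each hypothesis.
- Call the result an observational exposure–response association, and remove the mediation label for dose and timing in 5.3.2, 7.7.3 and the appendix table.
- If the severity interaction is kept, centre ISS and report it separately as effect modification.
- Reconcile the dose and timing definitions across the protocol hypotheses, 5.3.2 and 7.7.3 so that every day falls in exactly one bin. Either test the 2-hour contrast (SAP 4.1.2 says the application records time spent) or state that hypothesis 4 as written is not tested.

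Because the trial is complete, mark the change as made after data lock. The cost is a few sentences and a refit of the dose and timing models. The downsides are a weaker, non-causal label for an exploratory result, and less precision if the existing fit pooled both arms.

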## Research Activities

- 1. \* Provide a detailed description of all research activities (including screening and follow-up procedures) that will be performed for the purpose of this research study. This description of activities should be complete and of sufficient detail to permit an assessment of associated risks.**

Intervention and Control:

We have partnered with 3 national physician staffing groups. Cumulatively, these groups employ approximately 4500 physicians, cover  $\geq 30$  states, staff  $\geq 600$  emergency departments (EDs), and provide care to  $\geq 16$  million patients each year. We will ask physician leaders of the organizations, with which we have partnered, to distribute an email to their staff that describes the trial, and includes a link to the consent form. Physicians who provide consent will then receive a survey that collects demographic data which will allow us to assess eligibility.

Qualified physicians will be randomized with an allocation ratio of 1:1, based on a randomization schema generated by our statistician ([name]) in STATA 17.0 (Statacorp, TX) with blocks of 4 or 8.6. Trial coordinators will link the randomization schema to the enrollment data, and will assign participants to groups. Although we cannot maintain blinding after allocation, our data analysts will not have access to that information.

We will pre-load new iPads with Night Shift 2024 and will mail the devices to those allocated to the intervention group. We will ask participants to spend a minimum of two hours playing Night Shift 2024 within 2 weeks of receiving their device, and then return to the game for 20 minutes at 3, 6, and 9 months. Participants will keep their iPad as a fixed honorarium (approximate value: \$350), and will also receive a conditional monetary honorarium if they complete any of the booster doses that they complete (\$25/session). We will issue three email reminders and a phone call during the first two weeks after enrollment, and then quarterly reminders during the subsequent trial period. Participants have the option of not completing the assigned study task, but we do not have pre-specified criteria for discontinuing or modifying the allocated intervention.

Participants in the usual care group will complete outcome assessment tools, and will receive a conditional, wage-based honorarium (\$100/hour spent) upon completion of study tasks.

Interviews:

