4.1.1. Dosing and administration

Participants are asked to complete a minimum of 2 hours of gameplay within 2 weeks of receiving their device, followed by three 20-minute booster sessions at approximately 4, 7, and 10 months post-enrollment. Participants receive three email reminders and a phone call during the first two weeks, followed by quarterly reminders thereafter. A conditional honorarium of \$20 per completed booster session is provided. Participants also keep the trial iPad at the end of the year, as part of their honorarium.

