10. APPENDIX

10.1. Comparison of analytic elements across study documents.

Domain	DSMB protocol	Manuscript	Status	Rationale
Core Design Elements				
Primary outcome	Under-triage of severely injured patients (i.e., those with an ISS ≥ 16)	Under-triage of severely injured patients (i.e., those with an ISS ≥ 16)	Consistent	No change
Secondary outcomes	Over-triage; Mortality/readmission; Functional dependence*	Over-triage Mortality/readmission	*Deferred	SNF claims not available
Follow up	01/01–12/31/2024 (V1) 365 days (V1.2)	365 days	Consistent	No change
Analysis population	Intention-to-treat	Intention-to-treat	Consistent	No change
Unit of analysis	Patient	Patient	Consistent	No change
Statistical model	Mixed-effects logistic regression	Mixed-effects logistic regression	Consistent	No Change
Clustering	Physician-level and hospital-level random effects (V 1) Physician (V 1.4)	Physician-level	Consistent	No change
Covariate adjustment	Patient, physician, hospital (V1) None (V1.4)	None	Consistent	No change
Repeated measures	Sensitivity analysis	Sensitivity analysis	Consistent	N/A
Power calculation	Detailed	Overview only	Consistent	N/A
Alpha level	0.05	0.025	Deviation	Discussed in the methods
Sidedness of tests	One-sided	Two-sided	Deviation	Discussed in Methods
Multiplicity control	Not done	Not done	Consistent	N/A
Reporting and Secondary Analyses				
Effect modification	Sex, race, attitudes to video games	Sex, race, attitudes to video	Consistent	Simplify manuscript
Mediation analysis	Dose, game use–time to treatment of patients	Dose, game use–time to treatment of patients	Consistent	No change
Mediation analysis	Fidelity of intervention receipt	Not done	Not performed	Statistical package not available
Mediation analysis	Effect of under-triage on clinical outcomes	Not done	Not performed	No difference in clinical outcomes

Domain	DSMB protocol	Manuscript	Status	Rationale
Sensitivity analyses	None (version 1) Multiple (version 1.7)	Multiple	Expanded	Increase rigor

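### Exploratory dose (0–4 periods with any play) is not tied to the patient's visit date, so sessions played after the visit may be counted; the timing bands in SAP 7.7.3 and 5.3.2 also conflict

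*SAP*

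**What the plan says.** Dose. Up to Version 1.5, dose was two hours or more of play against less. The Version 1.5 deviation in SAP 7.7.3 replaces this: "We also reconceptualized dose as the number of intervention periods during which game play occurred for any amount of time (out of 4 total". SAP 5.3.2 words it as "participation in game usage during each intervention period for any amount of time (4 total". Section 7.7.3 adds: "Dose therefore represented actual treatment and not assignment". Neither section says up to what date the periods are counted.

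Where dose is used. Section 7.7.3 models the probability of under-triage with an interaction between the mediator and the patient's injury severity. SAP 7.5 models the outcome at patient level, and the deviation note under 3.2.2 takes patients treated in the 365 days after the physician's enrollment. Each patient therefore needs a dose value.

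Periods. SAP 4.1.1 has an initial session and then "three 20-minute booster sessions at approximately 4, 7, and 10 months post-enrollment". The Protocol (Research Activities) asks participants to "return to the game for 20 minutes at 3, 6, and 9 months".

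Timing. In 7.7.3 the bands run up to 30 days, then "versus 39-90 days versus" more than 90, with a further group for no use. SAP 5.3.2 gives "first 30 days post-usage vs. days 30-89 versus 90+ days". The Protocol's fifth exploratory hypothesis (Study Aims) also uses 30–89 for the later band.

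Status. SAP 7.7 calls these analyses hypothesis-generating. The Revision History dates data lock October 1, 2025 and the dose change 10/3/25. The Appendix row "Dose, game use–time to treatment of patients" is marked consistent, with no change.

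**The concern.** Play after a patient's visit cannot have affected that patient's triage. If dose is a physician's total over follow-up, a patient seen in month 2 carries the same value as one seen in month 11, including sessions still months away at the time of the visit. The variable then describes how long the physician stayed engaged as well as what the physician had been exposed to. Engagement is self-selected, as the SAP acknowledges by describing dose as treatment actually taken. A dose gradient could reflect persistent physicians rather than more play, and misdated exposure could blur a real gradient. The direction of the net error cannot be settled from the documents.

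The timing analysis is the other half of the exposure question. Its bands decide which patients count as recently exposed, and the two SAP sections would code some patients differently.

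What is at stake is the reading of the dose and timing results. The stated reason for the dose change was a better understanding of mediation.

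**Working it through.** The plan states no figure on this point to reproduce. Two checks apply.

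**Check 1: dose delivered by the visit against a whole-follow-up count.** Inputs from the documents: four periods (SAP 5.3.2, 7.7.3); boosters at 4, 7, 10 months (SAP 4.1.1) or 3, 6, 9 months (Protocol); a window of 365 days, taken as 12 months. Assumptions not in the documents: the count runs over the whole follow-up, visits are spread evenly, and the physician plays in all four periods exactly on schedule, starting on day 0. Every patient of that physician is then coded 4.

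Mean delivered dose = sum of (sessions played so far × months in that segment) / 12. Share of patients seen before the last session = month of last booster / 12.

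| Schedule | Segment lengths (months) | Mean delivered dose | Seen before last session |
|---|---|---|---|
| SAP 4, 7, 10 | 4, 3, 3, 2 | (1×4 + 2×3 + 3×3 + 4×2)/12 = 27/12 = 2.25 | 10/12 = 83% |
| Protocol 3, 6, 9 | 3, 3, 3, 3 | (1×3 + 2×3 + 3×3 + 4×3)/12 = 30/12 = 2.5 | 9/12 = 75% |

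Moving the first session to day 14, the end of a two-week allowance if the device arrived on day 0, lowers the means slightly, to 2.21 and 2.46. The shares do not change.

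If dose is instead counted up to each visit, the misdating disappears, but dose becomes bounded by time. A value of 4 is then possible only in the last 2/12 = 17% (SAP schedule) or 3/12 = 25% (Protocol schedule) of the window.

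**Check 2: timing bands, day by day since last use.**

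| Day | SAP 7.7.3 | SAP 5.3.2 |
|---|---|---|
| 30 | first band | first or second band |
| 31–38 | no band | second band |
| 39–89 | second band | second band |
| 90 | second band | third band |
| 91 and later | third band | third band |

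Taken literally, 7.7.3 leaves 8 days without a category and puts no day in two. Section 5.3.2 leaves none out, but day 30 falls in two bands unless its first band means days 0–29.

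With evenly spread visits, the gap in 7.7.3 would hold 8/365 = 2.2% of visits if only one session is played. It would hold 4 × 8 = 32 days, or 32/365 = 8.8%, if all four are played and time runs from the latest use.

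**The case against.** The strongest objection is that the SAP never says the count runs over the whole year. The maximum of four may give only the range of the score. The companion variable in 7.7.3 is dated relative to the patient's visit, so the authors had visit-relative dating in mind. This stands: a count up to the visit is not excluded, and every figure in Check 1 is conditional on the other reading. What remains is that one exposure variable is anchored to the visit in the text and the other is not.

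The size is also an upper case. It describes a physician who plays in every period on schedule, and the documents give no adherence data. That is fair too.

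The timing gap is probably a slip of the pen. Section 5.3.2 and the Protocol both have 30–89, so a reader should not infer that patients at days 31–38 were deliberately left out. The two SAP sections still disagree.

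A reader might also infer that the dose change was driven by results, since it follows data lock and Version 1.5 mentions results elsewhere. The documents do not support that. The remark about results sits in the separate entry on removed analyses, and 7.7.4 ties it to mediation of clinical outcomes. The dose entry has its own rationale.

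Nor is the change concealed. It is labelled a deviation in 5.3.2 and 7.7.3 and listed below the data-lock line. The Appendix compares the amended protocol with the manuscript, so marking the row consistent is defensible. However, the follow-up, clustering and covariate rows show their version changes and the dose row does not.

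**Conclusion.** The concern holds in a limited form. The Version 1.5 dose is not tied to the visit date. Its natural reading is one count per physician, which credits early patients with later play. On that reading, with evenly spread visits and full on-schedule play, 83% or 75% of a fully adherent physician's patients precede the last counted session, and the mean delivered dose is 2.25 or 2.5 against a coded 4. With less than full adherence the figures would differ, and the documents do not allow them to be estimated. The stronger statement, that the plan assigns post-visit sessions to patients, goes beyond the text.

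The conflict between the timing bands in 7.7.3 and 5.3.2 needs no assumption. The booster months differ between the two documents, so the boundaries of the periods being counted are also unsettled.

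All of this concerns exploratory analyses already labelled as such. The primary intention-to-treat comparison is unaffected.

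**What to change.** - State the counting window in 5.3.2 and 7.7.3. Compute dose per patient, from the app's time-stamped usage records, as the number of periods with play before that patient's visit. SAP 4.1.2 says the app logs use automatically, and the timing analysis already needs dates of play.
- Adjust this model for time since enrollment, because the count rises mechanically with follow-up. Dose will be partly collinear with that term, so expect a less precise estimate, and say so.
- Use one exhaustive, non-overlapping set of timing bands in both sections, for example up to 30 days, 31–89, 90 or more, and no use before the visit.
- Report the two-hours-or-more against less-than-two-hours analysis alongside. Describe the new dose as defined after data lock and not randomised.
- Show the Version 1.5 dose change in the Appendix row, as other amended rows do.
- Reconcile the booster months in the SAP and the Protocol, since they define the periods.

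The cost is a small recode of usage data, a rerun of an exploratory model, and SAP wording. If dose was in fact already counted up to the visit, the dose item reduces to saying so and adding the time adjustment.
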